BP Management System User Acceptance Testing

Study Protocol
NCT04688450

March 14, 2022
Version 4.1

**PARTNERS HUMAN RESEARCH COMMITTEE
DETAILED PROTOCOL
March 14, 2022 Version 4.1**

P.1. BACKGROUND AND SIGNIFICANCE

Historical background

Clinicians are not good at following blood pressure (BP) management guidelines. In an observational report from a California ICU by Hawryluk et al. [1 on Section P.10], 100 patients being managed with acute spinal cord injury were examined, and 42% of the documented MAP values were below the goal range, i.e., < 85mmHg. This notable failure to manage hypotension adequately after ASCI is consistent with other reports [2 on Section P.10].

Previous pre-clinical or clinical studies

Our own group studied BP patterns in ICU patients receiving continuous vasopressor infusions in two different hospitals, and found that many patients suffered episodes of sustained (>15 min) hypotension (< 60 mmHg) without any clinical event documented, nor any timely response [3 on Section P.10].

Because of this clinical need, we developed the VIGORIS system. VIGORIS is a software system that tracks BP through time and generates alerts whenever BP is forecast to drift outside of a pre-specified goal range. It is intended for use in patients receiving continuous vasopressor infusion to treat hypotension. In simulation analysis, using actual clinical data from ICUs of two different hospitals, the VIGORIS forecast algorithm predicts hypotension on average 10 min before sustained hypotension developed [3 on Section P.10].

Rationale behind the proposed research and potential benefits

However, the actual clinical value of this software system remains speculative. In the current study, we aim to run the investigational system during clinical care, and obtain user feedback about the usefulness of the decision-support functionality.

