- h. As well the research staff member will ensure that the nurse adjusts the investigational system's MAP and SBP goals, if these are ordered to be changed during the protocol.
 - i. The Technical Observer will document any identifiable interventions of events that have any effect on the patient's blood pressure or heart rate. When the Technical Observer perceives any substantial changes in the subject's hemodynamics, a time-stamped annotation will be made for the perceived cause. The goal is to have these events documented with very precise temporal resolution, i.e., down to the precise minute that the events occur. The Technical Observer may ask the nurse to clarify what intervention is occurring; by protocol, Technical Observer will not ask this clarification if there is any perception that time-sensitive interactions being delivered and/or if the nurse is discussing patient management with any other clinical team member. The Technical Observer will never suggest intervention or recommend any clinical care for the patient.
 - j. If the primary nurse-subject (who provided consent) takes a break and there is a temporary substitute nurse, we will turn off the display so that the investigational software cannot affect decision-making (except if the substitute nurse has been a nurse-subject for this study for a different ICU patient having completed the full protocol within the past 30 days; under that condition, we will continue the protocol during the break). If the primary nurse-subject break lasts longer than 60 min, we will terminate that enrollment.
 - k. The investigational software will be terminated one hour before the Technical Observer is scheduled to depart for the day, or one hour before the end of the consenting nurse's shift, or a maximum of 8 hours (whichever is shorter). After each subject enrollment, the apparatus will be removed from the care area and cleaned with an antibacterial wipe. The System hardware will be inspected to ensure there are no visible abnormalities such as evidence of spills or physical damage.

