- Question 3C (if answer “yes” to 3A): Do you perceive that the confusing or inaccurate display output could possibly lead to any patient management error?
- Question 4A: This system provides lots of visual information, which might be distracting. At any time, did the system actually distract you from noticing something important about your patient or administering important care to your patient, such that your response to the patient was delayed?
- Question 4B (if answer “yes” to 4A): If so, what?
- Question 5: Any other ideas about what could be improved, and how?
- Question 6: If we want to hold a catered lunchtime focus group to discuss possible modifications to the system, would you be willing to join for 20 minutes, so we can get your feedback?

P.6 BIOSTATISTICAL ANALYSIS

Specific data variables being collected for the study

- Survey results from clinicians
- Annotation of any technical issues observed by Technical Observer
- System database archive of measured vital-signs and associated vital-sign forecasts
- Any error- and critical-level log statements from the server log file
- Any error- and critical-level log statements from the UI log file

Study endpoints

Subjects will be enrolled during periods when the study staff are available to conduct the protocol for a minimum of four hours of data collection (plus an extra hour for apparatus cleaning as well as conducting the post-enrollment clinician survey). The maximum duration of data collection for a given subject will be eight hours, i.e., the duration of a shift for the study staff.

Statistical methods

There will be two aspects to the data analysis: “clinician perceptions” and “technical operation”.

For the clinician perception, we will pool the feedback results from Questions 1-4. We will report quantitative responses for Questions 1, 3A, 3C, and 4A.

For Questions 2, 3B, 4B, and 5, we will employ an “exploratory sequential mixed methods design” whereby we use the results of the questionnaires to form variables that represent the most common qualitative answers, then code the questionnaire responses according to those variables, yielding quantitative results for the user perception survey data, to supplement the free-text feedback.

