For assessing technical operation, we will rely on (a) real-time error surveillance by the Technical Observer who watches the system during investigational use; the Technical Observer will document any unexpected technical issues in terms of run-time issues, connectivity issues, or any other issues; (b) Retrospective data review to ensure the completeness and accuracy of electronic data collected by the research software system; and (c) Analysis of log data the server log file and UI log file to confirm an absence of error-level and critical-level log statements.

We will generate descriptive statistics associated with (a) proportion of time that the patient’s BP is maintained within the goal range; and (b) descriptive statistics of the MAP prediction algorithm including mean prediction error, and also, clinical events that were associated with temporal windows with the highest prediction errors (i.e., top quartile of prediction error). The proportion of time that the patient’s BP is maintained within the goal range will be used for future study design. The results about the clinical events associated with the highest prediction errors will be used for potential future enhancements to the prediction methodology. We will review log files to confirm that there are no error- nor critical-level log events (except for those that are expected to naturally occur during system shut-down, which would be after each patient-subject data collection session has been completed).

As is routine for research studies, we will also aggregate subject characteristics in our analysis. These data will be obtained from the electronic medical record (EMR). Data will include routine demographics, co-morbidities, and clinical details of the index ICU stay such as clinical pathologies and clinical interventions. As this chart review is planned to occur at a time subsequent to the main investigational protocol, we will also record two patient identifiers (MRN and name) to ensure we have the correct identity of the subject. These identifiers will be digitally erased no later than 12 months after data collection has been completed. A hardcopy of the identifier will be kept by the PI in a locked cabinet in his MGH office for long-term storage, for any unforeseen need to re-identify the subjects for purposes of obtaining additional data from the EMR.

Power analysis (e.g., sample size)

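### P.6 reports the MAP forecast's own error with no reference forecast, so it cannot show whether the forecast improves on carrying the current MAP forward; a benchmark from the archived data would be nearly free

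*Combined protocol and SAP*

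**What the plan says.** The second half of P.6, Statistical methods, promises two descriptive summaries: time in the BP goal range, and "descriptive statistics of the MAP prediction algorithm including mean prediction error". Under the second it will also examine "clinical events that were associated with temporal windows with the highest prediction errors (i.e., top quartile of prediction error". It gives that review a purpose: "The results about the clinical events associated with the highest prediction errors will be used for potential future enhancements to the prediction methodology".

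The list of variables at the start of P.6 includes the "System database archive of measured vital-signs and associated vital-sign forecasts". P.5, item i, adds that when the Technical Observer sees a substantial hemodynamic change, "a time-stamped annotation will be made for the perceived cause".

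The documents do not state a reference forecast, a skill measure, the forecast horizon, the window length, whether error is signed or absolute, or any target for it.

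**The concern.** A forecast error in mmHg is hard to read without the error of having no forecast. The system is a secondary display (P.7), so the nurse already has the current MAP. P.1 says that "the actual clinical value of this software system remains speculative". For the forecast part of the system, the natural benchmark is the MAP already on the monitor. A 3 mmHg error may be good in an unstable patient and worthless in a stable one.

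The same gap affects the window review. Windows ranked by raw error tend to be those in which MAP moved most, including many where the forecast came closer than the current MAP did. These windows feed changes to the algorithm, so the ranking rule matters. P.1 also discloses that the investigators invented the software and may benefit financially, which is a further reason to fix a neutral benchmark in advance.

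**Working it through.** The plan gives no error figure, horizon or MAP variability, so there is nothing of its own to reproduce. What follows is illustrative.

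**Inputs.** From the documents: the top-quartile rule, 20 sessions, and four to eight hours per session. Assumed: the MAP process, its SD and correlation time, and a 10-minute horizon. That horizon is borrowed from P.1 ("the VIGORIS forecast algorithm predicts hypotension on average 10 min before sustained hypotension developed"), which describes earlier simulation work and not this study's error horizon.

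**1. What the reference is.** Let x(t) be MAP when the forecast f is issued and h the horizon. Forecast error is e = x(t+h) − f. Carry-forward error is c = x(t+h) − x(t), which is the MAP change itself. For a best-possible forecast, e is uncorrelated with everything known at issue, so corr(e, c) = SD(e)/SD(c) = q. With normal errors, q is also the ratio of the two mean absolute errors, and 1 − q is the gain over carry-forward.

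**2. MAP that reverts to a mean (first-order autoregressive).** With r = exp(−10/τ), q = √((1+r)/2).

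| τ (min) | r | q | gain |
|---|---|---|---|
| 10 | 0.368 | 0.827 | 17% |
| 20 | 0.607 | 0.896 | 10% |
| 40 | 0.779 | 0.943 | 6% |

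At τ = 20 and SD 8 mmHg, carry-forward mean absolute error is 0.798 × 8 × √(2 × 0.3935) = 5.66 mmHg. The best-possible error is 0.798 × 8 × √(1 − 0.368) = 5.08 mmHg. Both scale with SD, so at SD 4 carry-forward gives 5.66/2 = 2.83 mmHg. Raw error would thus favour a no-skill forecast in the steadier patient over the best forecast in the more variable one.

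**3. MAP with persistent trend (Matérn-3/2, level and slope known at issue).** With u = √3·h/ℓ, Var(e) is proportional to 1 − exp(−2u)·[(1+u)² + u²], and Var(c) to 2·[1 − (1+u)·exp(−u)].
- ℓ = 10: u = 1.732, q = √(0.6725/1.0333) = 0.807, gain 19%.
- ℓ = 30: u = 0.577, q = √(0.1108/0.2290) = 0.696, gain 30%.
- A smoother variant, u = h/ℓ with ℓ = 30: u = 0.333, q = √(0.0302/0.0892) = 0.582, gain 42%.

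**4. Overlap of top-quartile error with top-quartile MAP change (simulated; 25% by chance).** It is 62%, 70% and 78% for the three autoregressive cases, and 59% and 49% for the first two trending cases. For the smoothest variant it is a little over 40%. In the autoregressive cases, the best-possible forecast beat carry-forward in about half of the top-quartile windows.

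**5. Twenty simulated sessions of mixed variability** (SD 3 to 9 mmHg, τ 15 to 60 min). Forecasts were set to explain a given share of the variance of MAP change. Skill here is 1 − MSE(forecast)/MSE(carry-forward).

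| skill set | raw mean absolute error (mmHg) | carry-forward error (mmHg) | skill recovered | overlap |
|---|---|---|---|---|
| 0 | 3.4 | 3.4 | 0.00 | 100% |
| 20% | 3.0 | 3.4 | 0.20 | 72% |
| 40% | 2.6 | 3.4 | 0.40 | 59% |
| 60% | 2.1 | 3.3 | 0.60 | 50% |

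Across sessions, mean absolute error correlated at least 0.99 with mean absolute MAP change at every skill level. At a fixed 40% skill, session errors still ran from about 1.3 to 4.5 mmHg. With failures planted in 10% of windows, about 20% of top-quartile windows were true failures.

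**6. Signed reading.** In the same simulation, mean signed error stayed within 0.01 mmHg of zero at every skill level. Even with drift it is small. Carry-forward errors telescope, so a 240-minute session with 230 windows and a net 10 mmHg drift gives about 10 × 10/230 = 0.43 mmHg for a forecast with no skill.

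**The case against.** The strongest reply is that the plan never asks this question. P.2 gives the aim as candid user feedback, and P.1 looks to that feedback to address the system's uncertain value. P.6 promises description only, its wording leaves room for further statistics, and the archive lets a reference be added at any time. All of this stands. It limits the point to an improvement in a secondary analysis, but permission to add a benchmark is not a commitment to report one.

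Two stronger readings might be inferred, and neither is supported.

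- *That the planned error mainly measures MAP movement and hardly reflects skill.* Read literally, a mean prediction error is signed and measures bias, not movement. For absolute error, the small 6% to 17% gain comes from assuming a mean-reverting process, which gives a forecaster little to work with. With persistent trend the gain is 19% to 42%, and in the mixed sessions raw error fell from 3.4 to 2.1 mmHg as skill rose from 0 to 60%.
- *That the plan cannot show where the algorithm failed.* High-error windows are linked to clinical events, and the Observer's time-stamped notes support attribution, although they too are prompted by hemodynamic change. Planted failures were enriched about twofold. A large swing that is missed is a real forecast failure.

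The remedy also has limits. If a flat forecast misses a sharp fall, then |e| = |c| and excess error is zero, so ranking by excess error alone would hide a missed event. Nurses see the display and may act on it, so a correct warning can score as an error. Nor does an error ratio measure the sensitivity and positive predictive value that P.5, item g, ties to the Index Threshold. These limits mean that the new ranking can only supplement the planned quartile.

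**Conclusion.** The point holds as a cheap improvement to a secondary descriptive analysis. Without a reference forecast, the planned figures cannot show whether the forecast improves on carrying the current MAP forward.

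If error is absolute or squared, its size and the selected windows depend heavily on MAP movement. The overlap is about 50% to 78% in most cases tried, and a little over 40% in the smoothest, against 25% by chance. If error is signed, the mean shows only bias. The plan does not say which form is meant.

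All of these sizes rest on assumed MAP processes and a 10-minute horizon. The absence of a reference does not depend on those assumptions. A reader should not infer that the study's main result is weakened: the user-feedback aim, the sample size and the safety rules do not depend on this analysis.

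**What to change.** Amend the forecast item in P.6, Statistical methods, as follows:

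1. State the forecast horizon, the window length and the form of the error.
2. For each archived forecast, compute the error of carrying forward the MAP at the time of issue, at the same horizon.
3. Report signed error and per-session mean absolute error for both forecasts, with the ratio of the mean absolute errors (1 minus the ratio is the gain).
4. Keep the planned top-quartile review, which is needed for missed events. Add a second set of windows ranked by excess error, that is, absolute forecast error minus absolute carry-forward error.
5. Note in the report that nurse action on the display can make a correct forecast look wrong.

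The cost is a few lines of analysis code and a short addition to P.6. No new data are needed, because measured values and forecasts are already archived. The one downside is that reported performance may look less favourable.

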- g. Active use of the System will be observed by a Technical Observer, i.e., an IRB-approved member of the investigative team. The Observer will generally observe the system continuously, with a minimum of at least one observation every 15 minutes. These observations provide additional assurance that there is no potential interference with any other aspect of the patient's care; that the technical performance of the System is grossly consistent with its intended operation; to ensure that the patient doesn't express any concern; and to ensure that the nurse doesn't express any concern. By protocol, if the nurse, patient, or patient family member states any negative perception of the investigational system, the Technical Observer will ask whether the nurse/patient/family member prefers the protocol to stop, and will oblige if this is requested. If the protocol is stopped early by request of the nurse, patient, or family member, the Technical Observer will ask for feedback after stopping the protocol and removing the apparatus: "You requested that we stop our testing protocol. Can you tell us why, to help us ensure that this testing protocol is safe and appropriate for other ICU patients?" The protocol will also terminate early if an Exclusion criterion is met: receiving two simultaneous vasopressors running at maximum doses (per the ICUs own protocols) or who is on one maximum-dose vasopressor and has a contraindication to receiving a second vasopressor (e.g., insufficient vascular access). During the protocol, the nurse will have the option to adjust the Index Threshold per their clinical practice preferences, and the Technical Observer will provide technical support of the nurse decides to do this. Lower thresholds for the Index Threshold provide higher sensitivity and earlier warnings at the expense of reduced positive predictive value. Higher thresholds the Index Threshold provide lower sensitivity and less advanced notifications at the benefit of

higher positive predictive value. Within the second hour of the protocol session, the Technical Observer will explicitly confer with the nurse about the operation of the system, confirming whether the nurse understands the visual display elements, whether the nurse would like to adjust the Index Threshold, and whether the nurse has any concerns about the investigational display or the protocol. This check-in will occur at a time when the nurse is not occupied with direct patient care.

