All adverse events will be recorded.

All adverse events (AEs) must have their relationship to study intervention assessed by the investigator who will evaluate the subject based on the temporal relationship and his/her clinical judgment. The degree of certainty about causality will be graded using the categories below. In a clinical trial, the study product must always be suspect.

- Definitely Related – There is clear evidence to suggest a causal relationship, and other possible contributing factors can be ruled out. The event must be phenomenologically definitive.
- Probably Related – There is evidence to suggest a causal relationship, and the influence of other factors is unlikely.
- Potentially Related – There is some evidence to suggest a causal relationship (e.g., the event occurred within a reasonable time after administration of the trial medication). However, other factors may have contributed to the event (e.g., the participant's clinical condition, other concomitant events). Although an AE may rate only as "possibly related" soon after discovery, it can be flagged as requiring more information and later be upgraded to "probably related" or "definitely related", as appropriate.
- Unlikely to be related – A clinical event whose temporal relationship to study intervention administration makes a causal relationship improbable (e.g., the event did not occur within a reasonable time after administration of the study intervention) and in which other drugs or chemicals or underlying disease provides plausible explanations (e.g., the participant's clinical condition, other concomitant treatments).
- Not Related – The AE is completely independent of study intervention administration, and/or evidence exists that the event is definitely related to another etiology. There must be an alternative, definitive etiology documented by the investigative team.

In this ICU population, expected adverse events will be episodes of hypotension (indeed, the motivation for the investigational device is a tool to reduce the frequency of observed sustained episodes of hypotension within the ICU). As well, unscheduled multiclinician responses and tachyarrhythmias are also expected in an ICU patient population receiving vasopressors.

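### P.6 describes clinical events only in the top quartile of prediction error, so it cannot show which events go with error, and its mean error mixes treated and untreated windows.

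*Combined protocol and SAP*

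**What the plan says.** The protocol's Statistical methods text in P.6 plans "descriptive statistics of the MAP prediction algorithm including mean prediction error" and a description of "clinical events that were associated with temporal windows with the highest prediction errors (i.e., top quartile of prediction error"). It gives the second output a use: the results on "clinical events associated with the highest prediction errors will be used for potential future enhancements to the prediction methodology". No other section adds an event rate for the lower three quartiles or over all windows, and none splits prediction error by whether the patient was treated between the forecast and its target time.

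Four other parts of the protocol bear on this:

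- **Live display.** P.1 says the system "generates alerts whenever BP is forecast to drift outside of a pre-specified goal range". P.9 says "the motivation for the investigational device is a tool to reduce the frequency of observed sustained episodes of hypotension within the ICU". P.5 step j switches the display off for most substitute nurses, to keep it from influencing decisions.
- **Background events.** P.9 expects hypotension in these patients and adds that "unscheduled multiclinician responses and tachyarrhythmias are also expected in an ICU patient population receiving vasopressors".
- **Data collected.** P.5 has the Technical Observer annotate clinical interventions and aims for timing to the minute. P.6 lists an archive of measured vital signs with their forecasts, and a later EMR review of "clinical details of the index ICU stay such as clinical pathologies and clinical interventions".
- **How annotation happens.** Under P.5 step g, "The Observer will generally observe the system continuously", with a floor of one observation every 15 minutes. Under step i, a perceived substantial hemodynamic change prompts a time-stamped note of its apparent cause.

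**The concern.** There are two separate gaps.

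**No comparison.** Saying that an event type is associated with high error requires its frequency where error is not high. Events that P.9 already expects in this population can fill a top-quartile list without any relation to forecast error. A developer working from that list could try to correct the algorithm for something that is merely common.

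**No split.** The nurse sees the forecast before the outcome occurs. If a forecast of low MAP is right and the nurse acts, the observed MAP ends above the forecast and the window is scored as an error. Read as algorithm failure, a useful warning would count against the method.

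What is at stake is the direction of later algorithm development. No decision rule in the protocol depends on these outputs.

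**Working it through.** The plan gives no forecast-error figure to reproduce. All error magnitudes, window lengths and intervention rates below are assumptions for illustration.

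**1. What a top-quartile rate alone can show**

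Let p_top and p_rest be the proportions of windows containing the event in the top quartile and in the other three. The ratio is p_top / p_rest. The share of all event windows lying in the top quartile is 0.25 p_top / (0.25 p_top + 0.75 p_rest). With p_top = 60%:

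| p_rest | ratio | share of event windows in top quartile |
|---|---|---|
| 10% | 6.0 | 0.15 / 0.225 = 67% |
| 20% | 3.0 | 0.15 / 0.30 = 50% |
| 40% | 1.5 | 0.15 / 0.45 = 33% |
| 60% | 1.0 | 0.15 / 0.60 = 25% |

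The stated output is 60% in every row. The last row is no association at all.

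**2. What a pooled mean can hide**

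Define error as forecast minus observed. If 20% of windows have an intervention with mean error −10 mmHg and the rest average +2, the pooled mean is 0.2 × (−10) + 0.8 × 2 = −0.4 mmHg. Neither component is visible.

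**3. How large the intervention effect might be**

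Assume untreated MAP has SD 8 mmHg, forecast error has SD 6, the lower limit is 10 mmHg below mean MAP, 80% of below-limit forecasts are acted on, and each action raises MAP by 10. The result turns on how forecast and outcome are related, which the documents do not state.

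*Model A: forecast = untreated MAP + independent noise.*
- The forecast SD is √(64 + 36) = 10. The treated share is 0.8 × Φ(−10/10) = 0.8 × 0.159 = 12.7%.
- This forecast is miscalibrated at the extremes. Treated windows have mean error −5.5 before any treatment effect, so about a third of their final mean of −15.5 comes from the model and not from treatment.

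*Model B: untreated MAP = forecast + independent noise (calibrated).*
- The forecast SD is √(64 − 36) = 5.29. The treated share is 0.8 × Φ(−10/5.29) = 0.8 × 0.0294 = 2.35%.

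In both models the shift in the pooled mean is the treated share × (−10). The other rows come from simulation, with windows ranked on absolute error:

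| | Model A | Model B |
|---|---|---|
| Pooled mean error (untreated 0.0) | −1.3 | −0.2 |
| Pooled MAE (untreated 4.8) | 6.0 | 4.9 |
| Intervention windows, share of top quartile | 47% | about 6% |
| Intervention windows, share of other three quartiles | 1% | 1% |
| No-intervention windows: mean, MAE | +0.8, 4.6 | 0.0, 4.8 |

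Varying the MAP SD, the proportion acted on (50–100%) and the effect (5–15 mmHg), the top-quartile share is 20–75% under model A (SD 6–10) and 2–37% under model B (SD 8–10; at SD 6 a calibrated forecast has no variance left). Both models also simplify the trigger: P.5 step g gives the nurse an adjustable Index Threshold.

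**4. Precision of the proposed comparison**

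Twenty sessions of 4 to 8 hours give 80 to 160 hours if all are completed. With assumed windows of 15 to 5 minutes, n runs from 80 × 60/15 = 320 to 160 × 60/5 = 1,920. For an event in 60% of windows, the 95% half-width for top quartile versus rest is 1.96 × √[DE × 0.24 × (1/(n/4) + 1/(3n/4))], where DE is the design effect:

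- DE = 1: 12.4 points at n = 320, 5.1 at n = 1,920.
- DE = 3 (assumed, for windows within patients): 21.5 and 8.8 points.

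**The case against.** The strongest reply is that this is a review of failures for generating ideas. P.6 calls it descriptive and speaks only of potential enhancements. Examining the worst cases needs no control group unless association is claimed, and an intervention that precedes a large error can be recognised from the annotations. This stands for single windows. It does not supply a background rate, and it leaves the pooled mean mixed.

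A second reply is that the list of statistics is open-ended, so MAE or RMSE is not excluded; that the highest errors probably means largest in absolute size; and that definitions may be in IDE sections not included here. All of this stands. The gap is what P.6 states, not what it forbids.

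A third reply is that the comparison has its own bias. Because step i annotations are partly prompted by abrupt hemodynamic change, they may be denser where forecast error is large, and the comparison could then show an association produced by ascertainment. The general duty to annotate any intervention softens this, but the guaranteed observation interval is only 15 minutes. This objection stands in full and has to be written into the fix.

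A reader might infer that much of the top quartile will consist of forecasts that were right and acted on. The documents do not support this: the 47% depends on a miscalibrated forecast model, and a calibrated one gives about 6%. A reader might also infer that windows without an intervention reveal the algorithm's true accuracy. They do not, because intervention follows the forecast and may be prompted by it.

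**Conclusion.** The point holds in a limited form. As stated, the event output cannot show whether an event type goes with high prediction error; this follows from the text and needs no assumption. Forecasts shown live can also turn a correct, acted-on warning into apparent error in the pooled mean. The direction of that effect is clear where treatment raises MAP, but its size is unknown: the intervention share of the top quartile ranges over 20–75% or 2–37% depending on an assumed forecast model, and neither range estimates this device's performance.

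A reader might infer that the study's conclusions are compromised or that needed data are missing. Neither follows. The specific aim in P.2 is user feedback, no decision rule uses these outputs, and the data for both analyses are already collected. Importance is low, and the change is worth considering, not essential.

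**What to change.** Add a few sentences to Statistical methods in P.6:

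1. Rank windows on absolute prediction error. Report the frequency of each event type in the top quartile beside its frequency in the other three, with intervals that allow for windows grouped within patients. State that step i annotations are partly triggered by substantial hemodynamic change, so the comparison may be inflated by ascertainment. Where possible, repeat it with events identified independently of that trigger, for example interventions recorded in the EMR.
2. As a descriptive supplement, report signed mean error and MAE overall and separately for windows with and without an intervention between forecast and target time, showing windows of uncertain status as such. State that the strata are selected and do not estimate accuracy for the untreated course.

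The cost is modest programming and no new data collection. Intervals will be wide (about 5–12 points if windows are independent, 9–22 with a design effect of 3), the strata will be smaller and noisier than the pooled data, and some ascertainment bias will remain. The analysis could be added later, but stating it beforehand avoids choosing the comparison after seeing the errors.
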